13.8 Analysis of Secondary Endpoints

13.8.1 Safety

Assessments of safety and tolerability will be performed on an ongoing basis. At the conclusion of the study, safety data will be summarized for each treatment arm within each cohort. The proportions of subjects with grade-3 or higher adverse events will be presented with exact binomial confidence intervals. Although it is unexpected after a successful early safety assessment, if at any time after the early safety review 33% or more of patients in a cohort are observed with severe toxicities, the regimen in that cohort will pause and a comprehensive safety analysis will be conducted.

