1. OBJECTIVES

1.1 Primary Objectives

NSCLC Cohort:

1. To assess safety and tolerability of combined checkpoint blockade with MEDI4736(durvalumab) and tremelimumab alone or with high or low-dose radiation in NSCLC
2. To compare the overall response (excluding the irradiated lesion(s)) between combined checkpoint blockade with MEDI4736 and tremelimumab alone or combined checkpoint blockade with low or high dose radiation.

Colorectal Cohort:

1. To assess safety and tolerability of combined checkpoint blockade with MEDI4736 and tremelimumab with high or low-dose radiation
2. To determine the overall response rate (excluding the irradiated lesion(s)) with combined checkpoint blockade with MEDI4736 and tremelimumab with either low or high dose radiation.

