5.4 Duration of Therapy

In the absence of treatment delays due to adverse event(s), treatment may continue for 12 months or until one of the following criteria applies which would prompt permanent discontinuation of study treatment:

- Disease progression
- Intercurrent illness that prevents further administration of treatment
- Unacceptable adverse event(s), as defined in Section 6.
- Patient decides to withdraw from the study
- General or specific changes in the patient's condition render the patient unacceptable for further treatment in the judgment of the investigator
- Patient non-compliance
- Pregnancy
 - All women of child bearing potential should be instructed to contact the investigator immediately if they suspect they might be pregnant (e.g., missed or late menstrual period) at any time during study participation.
 - The investigator must immediately notify CTEP in the event of a confirmed pregnancy in a patient participating in the study.
- Termination of the study by sponsor
- The drug manufacturer can no longer provide the study agent

The reason(s) for protocol therapy discontinuation, the reason(s) for study removal, and the corresponding dates must be documented in the Case Report Form (CRF).

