5.5 Duration of Follow Up

Patients will be followed for at least 12 weeks after removal from study treatment or until death, whichever occurs first. Patients removed from study treatment for unacceptable adverse event(s) will be followed until progression. All patients will be followed for at least a year from the time of initiation of treatment.

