7.4.3 Expedited Reporting Guidelines

Use the NCI protocol number and the protocol-specific patient ID assigned during trial registration on all reports.

Note: A death on study requires both routine and expedited reporting, regardless of causality. Attribution to treatment or other cause must be provided.

Death due to progressive disease should be reported as **Grade 5 “Disease progression”** in the system organ class (SOC) “General disorders and administration site conditions”. Evidence that the death was a manifestation of underlying disease (*e.g.*, radiological changes suggesting tumor growth or progression: clinical deterioration associated with a disease process) should be submitted.

Phase 1 and Early Phase 2 Studies: Expedited Reporting Requirements for Adverse Events that Occur on Studies under an IND/IDE within 30 Days of the Last Administration of the Investigational Agent/Intervention ^{1,2}

FDA REPORTING REQUIREMENTS FOR SERIOUS ADVERSE EVENTS (21 CFR Part 312) NOTE: Investigators MUST immediately report to the sponsor (NCI) ANY Serious Adverse Events, whether or not they are considered related to the investigational agent(s)/intervention (21 CFR 312.64) An adverse event is considered serious if it results in ANY of the following outcomes:
 
 1) Death 2) A life-threatening adverse event 3) An adverse event that results in inpatient hospitalization or prolongation of existing hospitalization for ≥ 24 hours 4) A persistent or significant incapacity or substantial disruption of the ability to conduct normal life functions 5) A congenital anomaly/birth defect. 6) Important Medical Events (IME) that may not result in death, be life threatening, or require hospitalization may be considered serious when, based upon medical judgment, they may jeopardize the patient or subject and may require medical or surgical intervention to prevent one of the outcomes listed in this definition. (FDA, 21 CFR 312.32; ICH E2A and ICH E6). 		

ALL SERIOUS adverse events that meet the above criteria MUST be immediately reported to the NCI via electronic submission within the timeframes detailed in the table below.
		
Hospitalization	Grade 1 and Grade 2 Timeframes	Grade 3-5 Timeframes
Resulting in Hospitalization ≥ 24 hrs	10 Calendar Days	24-Hour 5 Calendar Days
Not resulting in Hospitalization ≥ 24 hrs	Not required	

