--	---

The following visits and assessments are required after discontinuing study treatment:

Days following discontinuation:

30, 60 and 90 days (+/-5 days): physical exam, vital signs, body weight, CBC with diff, serum chemistries^a, pregnancy test for WOCB (urine or serum) AE/SAE assessments, concurrent medications, and performance status

Cohort 2 – Colorectal cancer

	Pre- Study	Wk 1	Wk 2	Wk 3	Wk 4	Wk 5	Wk 6	Wk 7	Wk 8	Wk 9	Wk 10	Wk 11	Wk 12	Wk 13- 52	Off Treatment ^e
MEDI4736(durvalumab)		A				A				A				A	
Tremelimumab		B				B				B				B	
Radiation therapy			C				C				C			C	
Informed consent	X														
Demographics	X														
AE/SAE Assessments ^l	X	X				X				X				X ^e	X
Medical history	X	X				X				X				X ^e	
Concurrent meds ^d	X													X	
Physical exam	X	X				X				X				X ^e	X
Vital signs ^p	X	X				X				X				X ^e	X

Performance status	X	X				X				X				X ^e	X
CBC w/diff, plts	X	X ^b				X				X				X ^e	X
Serum chemistry ^a	X	X ^b				X				X				X ^e	X
EKG ^f	X														
Hepatitis B and C and HIV ^m	X														
Urinalysis	X ^f														
Tumor measurements	X		Tumor measurements should be performed during week 7-8 and then repeated every 12 weeks +/- 5 days. Documentation (radiologic) must be provided for patients removed from study for progressive disease.												
Radiologic evaluation ^k	X		Radiologic measurements should be performed during week 7 or 8 and then every 12 weeks +/- 5 days while on treatment.												X ^e
B-HCG	X ^b	X				X				X				X ^e	X ^e
Research blood samples	X					X									
Biopsy of site(s) of disease	X ⁱ								X ^j						
PRO-CTCAE ⁿ	X		X		X		X		X				X	X	X

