13.9 Reporting and Exclusions

13.9.1 Evaluation of Toxicity

All patients will be evaluable for toxicity from the time of their first treatment with MEDI4736 and tremelimumab with or without RT.

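### The untimed Grade 3+ proportion in section 13.8.1 is not comparable between arms if time on treatment differs; add cumulative incidence from first dose

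*Combined protocol and SAP*

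**What the plan says.** For NSCLC the first primary objective (section 1.1) is "To assess safety and tolerability of combined checkpoint blockade with MEDI4736(durvalumab) and tremelimumab alone or with high or low-dose radiation in NSCLC". The colorectal cohort has a matching objective for its two radiation arms.

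Section 13.8.1 gives the final analysis: "The proportions of subjects with grade-3 or higher adverse events will be presented with exact binomial confidence intervals". It states no time window or confidence level, and no person-time rate, time-to-event analysis or exposure summary. None of these analyses of toxicity appears elsewhere.

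The toxicity population in section 13.9.1 has an opening date but no closing date: "All patients will be evaluable for toxicity from the time of their first treatment".

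The section 10 calendars schedule AE assessment about every 4 weeks on treatment. After discontinuation the visits are at "30, 60 and 90 days (+/-5 days): physical exam, vital signs, body weight", with the list continuing to "pregnancy test for WOCB (urine or serum) AE/SAE assessments, concurrent medications, and performance status". No AE visit is scheduled after day 90.

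Under section 5.4, "treatment may continue for 12 months or until one of the following criteria applies"; the first criterion listed is disease progression. Section 5.5 adds: "All patients will be followed for at least a year from the time of initiation of treatment".

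Two reporting rules in section 7.4.3 bear on the count. Serious AEs more than 30 days after the last administration stay reportable, with no end date, if at least possibly related. And "Death due to progressive disease should be reported as" a Grade 5 event, which section 13.8.1 does not exclude.

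**The concern.** An ever/never proportion treats all patients as if watched equally long. Here the scheduled window is time on treatment plus about 90 days: roughly 3 months after one dose, and roughly 15 months (12 + 3) after a full course. Its length depends on when the disease progresses, which the trial hopes radiation will change.

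In the NSCLC cohort, readers will set each radiation arm's proportion beside the randomised control to judge whether radiation adds toxicity. If the arms differ in time on treatment, part of any difference, or of any apparent similarity, will reflect unequal observation. The exact binomial interval describes sampling error only and cannot show this.

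**Working it through.** **The plan's own toxicity figures.** Section 13.6 gives the probability of three or more affected patients among 10. The exact binomial tail at true rates of 10, 15, 20, 25 and 30% is 0.070, 0.180, 0.322, 0.474 and 0.617, against the stated 0.07, 0.18, 0.33, 0.47 and 0.62. The table reproduces, apart from 0.33, which would round to 0.32. It says nothing about unequal observation time.

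**Inputs from the plan.** Response is 5% (control) against 22% (radiation) with 40 per arm (section 13.4.1). Treatment lasts at most 12 months, taken as 52 weeks. The post-treatment tail is 90 days, or 12.86 weeks. Restaging is at week 7 or 8 and then every 12 weeks (section 10).

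**Assumptions, since the plan gives no Grade 3+ rate or treatment duration.** The hazard λ of a first Grade 3+ AE is constant and the same in both arms, set so that the control arm's crude proportion is 20, 30 or 40%. Responders stay on treatment 52 weeks. Non-responders stop at 8 weeks (first restaging) or 20 weeks (8 + 12, second restaging).

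**Formula.** For a patient on treatment T weeks, P = 1 − exp(−λ(T + 12.86)). An arm's proportion is ORR × P(responder) + (1 − ORR) × P(non-responder). The difference between arms is therefore (0.22 − 0.05) × [P(responder) − P(non-responder)].

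**One case in full.** Non-responders stop at 8 weeks and λ = 0.00985 per week.
- Non-responder: 1 − exp(−0.00985 × 20.86) = 0.186.
- Responder: 1 − exp(−0.00985 × 64.86) = 0.472.
- Control: 0.95 × 0.186 + 0.05 × 0.472 = 20.0%.
- Radiation: 0.78 × 0.186 + 0.22 × 0.472 = 24.9%.

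| Non-responders stop | Control | Radiation | Gap (points) |
|---|---|---|---|
| 8 weeks | 20% | 24.9% | 4.9 |
| 8 weeks | 30% | 36.1% | 6.1 |
| 8 weeks | 40% | 46.7% | 6.7 |
| 20 weeks | 20% | 22.6% | 2.6 |
| 20 weeks | 30% | 33.4% | 3.4 |
| 20 weeks | 40% | 44.0% | 4.0 |

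Mean windows are 23.1 against 30.5 weeks in the first three rows and 34.5 against 39.9 weeks in the last three. True toxicity is identical in every row.

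**Sensitivity to when toxicity occurs.** Here treatment time is exponential, capped at 52 weeks, and a control median of 2 months gives 30%.

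| Hazard | Median 3 months | Median 4 months | Median 6 months |
|---|---|---|---|
| Constant | 34.6% | 38.2% | 43.2% |
| Ends at week 26 | 31.6% | 32.5% | 33.5% |
| Ends at week 12 | 30% | 30% | 30% |

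The last row shows no gap because every window is at least 12.86 weeks, so all events are captured.

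**Sensitivity to progression deaths.** Suppose a fraction q of non-responders die of progression within 90 days of stopping, and each death counts as Grade 5. The non-responder proportion becomes 1 − (1 − q)(1 − P). With non-responders off at 8 weeks, the gap reaches zero at q of about 35% (20% base) or 50% (30% base), and is negative beyond that. If toxicity is early only, any q above zero puts the shorter-treated arm higher. At a 30% base and q = 20%, the non-responder value is 1 − 0.8 × 0.7 = 0.44. Control is then 0.95 × 0.44 + 0.05 × 0.30 = 43.3%, and radiation 0.78 × 0.44 + 0.22 × 0.30 = 40.9%.

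**The case against.** Four arguments weigh against the point.

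*The size is modest and the summary is descriptive.* No between-arm toxicity test is planned, and the colorectal cohort has no arm without radiation. At 30% against 36.1% with 40 per arm, the standard error of the difference is √(0.30 × 0.70/40 + 0.361 × 0.639/40), about 10.5 points, so the 6.1-point gap is about 0.6 standard errors. This stands, and it limits the priority. It does not make the arms comparable.

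*Early stopping is protected.* The early safety rule uses dose-limiting toxicities with a 4-week period common to all arms (section 5.2). This also stands. But Arm B receives radiation in weeks 2, 6, 10 and 14, so most of its radiation falls after that period, and the final summary has no equivalent safeguard.

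*AEs are not ignored after day 90.* A reader might infer from the calendar that nothing is captured later. That goes too far, since related serious AEs remain reportable and patients are followed for at least a year. However, that route covers only serious events judged at least possibly related, while section 13.8.1 counts all Grade 3+ AEs.

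*The direction is not fixed.* A reader might infer that a longer-treated arm must look more toxic by construction and an ineffective arm safer. The documents do not support this. Treatment is front-loaded: at most four tremelimumab doses and radiation no later than the fourth cycle, then durvalumab alone. Section 2.2 reports about 9% AE discontinuations and 6% related serious AEs for monotherapy, against 13 to 15% for each with the combination. Those figures are not time-adjusted, but they give no support to a flat hazard over 15 months. The Grade 5 coding of progression deaths pushes the other way.

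**Conclusion.** The concern holds in this form: with only an untimed proportion, an outcome-dependent stop and scheduled assessment ending 90 days later, the arms' Grade 3+ proportions are not comparable when time on treatment differs.

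Under the design's own response rates and one constant hazard, the artefact is about 2.6 to 6.7 points against the longer-treated arm. This rests on assumed Grade 3+ rates of 20 to 40% and assumed stopping times of 8 or 20 weeks for non-responders and 52 weeks for responders. With 30% in control, it is about 1.6 to 3.5 points if the hazard ends at week 26 and zero if it ends at week 12. It can change sign once progression deaths are counted. Gaps above 10 points, such as 30% against 43.2%, need both a constant hazard and a tripling of median time on treatment; nothing in the documents supports that combination.

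This is a worthwhile, inexpensive improvement to the reporting of a primary objective. It does not invalidate the safety monitoring.

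**What to change.** Keep the crude proportion and its exact interval, and add the following to section 13.8.1:

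- Per-arm cumulative incidence of first Grade 3+ AE from first dose, read at one common time that includes all scheduled tremelimumab and Arm B radiation, for example 6 months.
- Censoring at the end of AE ascertainment, with that end date stated.
- Death without a prior Grade 3+ AE treated as a competing event. Grade 5 disease progression is reported separately from toxicity, so the same death is not also counted as a toxicity event.
- Time on treatment by arm.

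A proportion within 90 days of first dose should not become the headline, although the day-90 visit makes it tempting. On schedule, cycle 4 starts on day 85 (3 × 28 + 1) and Arm B's fourth radiation course falls in week 14, days 92 to 98. That window would close about 5 days after the last tremelimumab dose and before Arm B's radiation is complete.

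The cost is SAP wording, one extra analysis and one table, on data already scheduled for collection. The drawback is some dependence on censoring: patients who stop early leave ascertainment before 6 months, often for reasons related to outcome, and the estimate assumes that patients still under assessment represent them. Showing time on treatment by arm lets readers judge that.

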7.3 Adverse Event Characteristics

- **CTCAE term (AE description) and grade:** The descriptions and grading scales found in the revised NCI Common Terminology Criteria for Adverse Events (CTCAE) version

4.0 will be utilized until March 31, 2018 for AE reporting. CTCAE version 5.0 will be utilized for AE reporting beginning April 1, 2018. All appropriate treatment areas should have access to a copy of the CTCAE version 5.0. A copy of the CTCAE version 5.0 can be downloaded from the CTEP web site

http://ctep.cancer.gov/protocolDevelopment/electronic_applications/ctc.htm.

- **For expedited reporting purposes only:**

- AEs for the agent that are ***bold and italicized*** in the CAEPR (*i.e.*, those listed in the SPEER column, Section 7.1.1) should be reported through CTEP-AERS only if the grade is above the grade provided in the SPEER.
- Other AEs for the protocol that do not require expedited reporting are outlined in section 7.4.4.

- **Attribution of the AE:**

- Definite – The AE *is clearly related* to the study treatment.
- Probable – The AE *is likely related* to the study treatment.
- Possible – The AE *may be related* to the study treatment.
- Unlikely – The AE *is doubtfully related* to the study treatment.
- Unrelated – The AE *is clearly NOT related* to the study treatment.

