7.4.4 Additional Protocol-Specific Expedited Adverse Event Reporting Exclusions

For this protocol only, the AEs/grades listed below do not require expedited reporting via CTEP-AERS. However, they still must be reported through the routine reporting mechanism (Section 7.4):

- Any grade 1 or grade 2 laboratory abnormality that resolves within 7 days. Any grade 1 or grade 2 laboratory abnormality lasting for more than 7 days without resolution will require Expedited Adverse Event Reporting.
- Any grade 1 or grade 2 adverse event attributed as not related to study treatment.
- Any grade 1 or grade 2 adverse event attributed as possibly related or related to study treatment and is expected and resolves within 14 days. Any grade 1 or grade 2 adverse event attributed as possibly related or related to study treatment and is expected which does not resolve within 14 days will require Expedited Adverse Event Reporting.

7.5 **Routine Adverse Event Reporting**

All Adverse Events **must** be reported in routine study data submissions. **AEs reported expeditiously through CTEP-AERS must also be reported in routine study data submissions.**

Adverse event data collection and reporting, which are required as part of every clinical trial, are done to ensure the safety of patients enrolled in the studies as well as those who will enroll in future studies using similar agents. AEs are reported in a routine manner at scheduled times during the trial using Medidata Rave. For this trial the Adverse Event CRF is used for routine AE reporting in Rave.

Clinician graded CTCAE is the AE safety standard. Patients will respond to PRO-CTCAE items in a manner to complement CTCAE reporting, but no real-time review nor protocol directed action will be taken. The patient reported data will be entered directly from the patient's device into the RAVE database and may be available for the review with routine AEs.

7.6 **Secondary Malignancy**

A *secondary malignancy* is a cancer caused by treatment for a previous malignancy (e.g.,

treatment with investigational agent/intervention, radiation or chemotherapy). A secondary malignancy is not considered a metastasis of the initial neoplasm.

CTEP requires all secondary malignancies that occur following treatment with an agent under an NCI IND/IDE be reported expeditiously via CTEP-AERS. Three options are available to describe the event:

- Leukemia secondary to oncology chemotherapy (e.g., acute myelocytic leukemia [AML])

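### As written, the final Grade 3+ adverse event proportion in 13.8.1 counts deaths from progression, because 7.4.3 has them recorded as Grade 5 events

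*Combined protocol and SAP*

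**What the plan says.** Section 1.1 lists safety and tolerability first among the primary objectives of both cohorts; 13.1.2 lists safety assessments as secondary endpoints. Section 13.8.1 says that safety data will be summarised by arm within cohort, and names one statistic: "The proportions of subjects with grade-3 or higher adverse events will be presented with exact binomial confidence intervals". No confidence level is given.

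The reporting rules decide what counts as an adverse event in the data:

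- 7.4.3: "A death on study requires both routine and expedited reporting, regardless of causality".
- 7.4.3: "Death due to progressive disease should be reported as" a Grade 5 event, term Disease progression, in the general disorders class.
- 7.5: "AEs reported expeditiously through CTEP-AERS must also be reported in routine study data submissions".
- 7.3 sets a five-level attribution scale, from unrelated to definite, and 7.4.3 adds for deaths: "Attribution to treatment or other cause must be provided".

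The same paragraph of 13.8.1 holds a later safety trigger: if "33% or more of patients in a cohort are observed with severe toxicities", the regimen pauses for a full safety analysis. The plan does not define that toxicity term.

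**The concern.** A patient who dies of cancer on study is, by the plan's own coding, a patient with a Grade 5 adverse event, and so belongs in the numerator of the one final safety proportion. These patients have progressed on, or not benefited from, earlier therapy (3.1.3), so such deaths will not be rare.

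Two things are at stake. First, the reported rate describes treatment harm and disease course together, and the reader cannot separate them. Second, the trial tests whether radiation improves response. If it does, and progression deaths fall, an RT arm would show a lower Grade 3+ proportion for that reason alone, which could hide toxicity added by radiation. If radiation has the opposite effect, that arm would look less safe with no difference in treatment harm.

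**Working it through.** **The text, side by side.** The plan separates disease from treatment harm in other places. The DLT definition in 5.2 leaves out toxicity clearly due to the primary disease. The response categories in 13.9.2 keep early death from malignant disease apart from early death from toxicity. Section 7.3 grades attribution. Only 13.8.1 draws no such line, and with 7.4.3 and 7.5 its literal numerator includes progression deaths.

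**Which deaths are counted is also open.** The expedited table in 7.4.3 covers 30 days after the last administration, and its footnote asks for reports of later serious events only when attributed to treatment. The study calendar has AE visits at 30, 60 and 90 days after discontinuation. Follow-up lasts at least a year from the start of treatment (5.5). Section 13.9.1 says when toxicity evaluation starts but not when it ends.

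**No plan figure is in dispute.** The nearest is the table in 13.6. The binomial chance of 3 or more of 10 at true rates of 10, 15, 20, 25 and 30% is 0.070, 0.180, 0.322, 0.474 and 0.617, against the stated 0.07, 0.18, 0.33, 0.47 and 0.62. The 20% entry rounds to 0.32. None of this bears on the point.

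**Illustration of size.** Inputs:

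- r = 15%, the treatment-related severe event rate. This is a stand-in: 2.2.2.1 gives about 15% with a related serious AE on the combination (2.2.1 gives 13%). It is not a Grade 3+ rate.
- d = the share of patients with a recorded progression death, taken as independent of r. The documents give no value; 10 to 30% is assumed.
- n = 40 per NSCLC arm (13.3.1).

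Reported proportion = 1 − (1 − r)(1 − d). The intervals are exact 90%; that level is assumed.

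| d | Reported proportion | Patients of 40 | Interval |
|---|---|---|---|
| 0 | 15% | 6 | 0.07–0.27 |
| 10% | 1 − 0.85 × 0.90 = 23.5% | 9 | 0.12–0.36 |
| 20% | 1 − 0.85 × 0.80 = 32.0% | 13 | 0.20–0.47 |
| 30% | 1 − 0.85 × 0.70 = 40.5% | 16 | 0.27–0.54 |

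With r = 13% the last three proportions are 21.7%, 30.4% and 39.1%.

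**Difference between arms.** Give both arms r = 15%, with d = 30% in control and 20% in an RT arm. The proportions are 40.5% and 32.0%, a gap of 8.5 points with no difference in treatment harm. Conversely, with the same d values, an RT arm would match the control's 40.5% at a related rate of 1 − 0.595/0.80 = 25.6%, so about 10 points of added toxicity would not show.

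**Sensitivity to the window.** Suppose every patient progresses, treatment ends at progression, and survival after that is exponential with a median of 3 to 9 months (all assumed). Then 7–20% die within 30 days and 20–50% within 90 days. At r = 15% the reported proportion would be 21–32% for the 30-day window and 32–57.5% for the 90-day window. As not every patient progresses, these are upper ends.

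**The case against.** The strongest reply is that 13.8.1 reports adverse events, not toxicity. An any-cause Grade 3+ table is a standard, legitimate summary that avoids investigator judgement. Progression deaths carry their own term and an attribution, so they can be separated in any table, and the promise to summarise safety data leaves room to do so. A reader might infer that the plan labels cancer deaths as toxicity, or that attribution is not recorded. The documents support neither reading. What remains is that the one statistic named in advance does not make the separation, so the choice of numerator is left until results are known.

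A reader might also infer that the plan's safety monitoring as a whole is affected. The 3-of-10 rule in 13.6 is a numerical safety analysis too, and to the extent that it rests on the DLT definition in 5.2, disease-related toxicity is already left out.

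A third tempting reading is that progression deaths would trigger the 33% pause. That holds only if its toxicity term means any Grade 3+ adverse event, yet the sentence before it uses different words. On that reading, applied per arm at one look with r = 15%, the chance of reaching 14 of 40 would rise from 0.001 to 0.07, 0.40 and 0.81 at d = 10, 20 and 30%; for 10 of 30 it would rise from 0.01 to 0.15, 0.51 and 0.84. The text does not establish that reading. It shows only that the term is undefined.

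Two further points stand. No between-arm safety test is planned, and the 8.5-point gap above has a standard error of about 11 points at 40 per arm. And in an open-label trial, attribution is itself open to bias: RT arms have one more treatment to which an event can be attributed.

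**Conclusion.** The point holds as a defect of definition. Read literally, 13.8.1 with 7.4.3 and 7.5 puts deaths from progression into the only final safety proportion specified for a primary objective, so that proportion can move with efficacy.

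Its size cannot be computed from the documents. The range of about 24% to 41% reported against 15% related depends on a serious-event rate used as a stand-in, on independence, and on assumed death rates. A patient with another Grade 3+ event adds nothing by dying of progression, so overlap greater than independence implies would shrink the effect; a wider AE window would enlarge it. It should be settled before the safety data are summarised.

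**What to change.** In 13.8.1:

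1. Exclude the term Disease progression from the Grade 3+ proportion and report it separately by arm.
2. Present, with exact binomial intervals at a stated level, the proportion of treated patients with Grade 3+ events attributed as possible, probable or definite to any study treatment (drug or radiation), beside the any-cause proportion.
3. State the window over which adverse events are counted, the same in every arm.

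The any-cause proportion must stay alongside, because attribution is open-label and RT arms have the extra treatment.

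Separately, the toxicity term in the 33% pause rule must be reconciled with the DLT definition in 5.2 and the wording in 13.6. What that rule should count is for the investigators and the sponsor to settle.

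The cost is a few sentences and one more table column. Attribution and the separate term are already collected under 7.3 and 7.4.3, so no new data are needed.
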